#### **TARGET POPULATION**

#### **INCLUSION CRITERIA**

The following criteria must be met for study entry:

- An Informed Consent Form (ICF) for participation of the maternal subject and her infant (for collection of blood, infant demographic and adverse event data) is signed and dated by the subject. Where applicable, the written ICF with respect to the infant is also signed and dated by the holder of parental rights as designated by the maternal subject
- Woman is able and willing to comply with the study protocol, according to the judgment of the investigator, in particular:
  - Woman is willing to breastfeed (either exclusively, or with formula supplementation) for at least 60 days after the first postpartum ocrelizumab infusion (this decision is to be taken prior to and independent from study participation)
  - Woman is willing to provide breastmilk samples before and after their first and, if applicable, second postpartum ocrelizumab infusion
    - Note: Exposure to ocrelizumab includes administration of an initial split dose of two 300 mg infusions (in 250 mL 0.9% sodium chloride) separated by 14 days for women initiating treatment with ocrelizumab, or a single 600 mg infusion (in 500 mL 0.9% sodium chloride) for women already on treatment with ocrelizumab.
- Woman is between 18 and 40 years of age at screening
- Woman has a diagnosis of MS or CIS (in line with the locally approved indications)
- Woman has delivered a healthy term singleton infant (≥37 weeks gestation)
- Infant is between 2–24 weeks of age at the time of the mother's first postpartum dose of ocrelizumab
- For women who received commercial ocrelizumab (OCREVUS) before enrolment: documentation that last exposure to ocrelizumab occurred more than 3 months before the LMP (i.e., excluded a potential fetal exposure) and was given at the approved dose of 2×300 mg or 1×600 mg
- Woman agrees to use acceptable contraceptive methods or alternative methods during the study as described below and, if applicable, upon study treatment discontinuation, as defined by the local prescribing information

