ADID = average oral daily infant dosage; ASQ-3 = Ages and Stages Questionnaire, version 3; AUC = area under the milk concentration-time curve; CIS = clinically isolated syndrome; EDSS = Expanded Disability Status Scale; HBV = hepatitis B virus; Hib = Hemophilus influenzae type b; LLN = lower limit of normal; LMP = last menstrual period; MDID = maximum oral daily infant dosage; MMR = measles, mumps, and rubella MS = multiple sclerosis; PCV-13 = 13-pneumococcal conjugate vaccine; RID = relative infant dose; WHO = World Health Organization.

Table 1 Objectives and Corresponding Endpoints (cont.)

Objectives	Corresponding Endpoints	
Secondary Outcome Measures (cont.  • To evaluate the relative and maximum exposure to ocrelizumab in infants of lactating women with CIS or MS receiving ocrelizumab postpartum		
	Note: Other pharmacokinetic and exposure parameters may be calculated as appropriate, based on the data obtained.	
To evaluate whether there is transfer of ocrelizumab from the mother to the infant via breastmilk	Serum concentration of ocrelizumab in the infant measured at Day 30 after the mother's first ocrelizumab postpartum infusion	
To evaluate whether infants of lactating women with CIS or MS receiving ocrelizumab postpartum are able to mount humoral immune responses to clinically relevant vaccines	
 
Mean titers of antibody immune response(s) to common childhood vaccinations with full or partial doses given prior to 1 year, which include responses to MMR, diphtheria, tetanus, pertussis, Hib, HBV, and PCV-13
 
Proportion of infants with positive humoral response (seroprotective titers; as defined for the individual vaccine) to vaccines
 
	
Safety Objectives		
To evaluate the safety of ocrelizumab in lactating women with CIS or MS receiving ocrelizumab postpartum and in their respective infants	Rate and nature of adverse events in the mother throughout the study, including changes in clinical and laboratory results	
	
 
Rate and nature of adverse events in the infant throughout the study, including infections and hospitalizations
 
	

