### 6.6 SAFETY ANALYSES

# 6.6.1 Analyses of Exposure, Adverse Event, Laboratory, and Vital Signs Data

The safety outcome measures comprise the following: incidence and nature of all adverse events, including findings on vital sign measurements, neurological examinations, clinical laboratory tests, locally-reviewed MRIs conducted for safety reasons (non-MS CNS pathology), and concomitant medications.

All safety analyses will be conducted on data collected from the first postpartum ocrelizumab infusion until the end of the study. The safety analysis will be performed on the safety populations of women and infants separately. Safety will be assessed through summaries of adverse events (including rates/incidence rates and corresponding 95% CIs) and clinical laboratory abnormalities.

All adverse events will be summarized by mapped term, appropriate thesaurus level and toxicity grade, and tabulated by MedDRA system organ class (SOC) and preferred term for individual adverse events within each SOC. Grade 3–5 adverse events, serious adverse events, adverse events leading to treatment discontinuation, and time to withdrawal from the study due to an adverse event will be summarized. In addition, all serious adverse events and deaths will be listed.

Associated laboratory parameters, such as hepatic function, renal function, and hematology values, will be grouped and presented together.

Concomitant medications recorded during the study will be summarized using frequency tables.

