3.3 DATA MONITORING

There is no Independent Data Monitoring Committee (IDMC) planned for this study.

4. STATISTICAL METHODS

The analysis of this open-label study will be primarily based on descriptive statistical methods. Unless otherwise specified, statistical tests will be exploratory in nature. Corresponding 95% confidence interval (CI) will be presented as appropriate. No correction for multiple testing will be applied.

For continuous variables, descriptive statistics (e.g., number of patients [n], mean, standard deviation [SD], median, 25th and 75th percentiles, minimum, maximum) will be calculated and summarized.

For categorical variables, the number and percentage in each category will be displayed.

Unless specified otherwise, values at the mother's first ocrelizumab infusion visit (which may take place any time between Week 2 and Week 24 post-partum) will be considered as baseline for all analyses. For analyses in the infant, date of birth will be considered as baseline.

Note that the protocol's Schedule of Assessments (see Appendix 2) defines the day of first post-partum ocrelizumab administration as Day 0, whereas per the Clinical Data Interchange Standards Consortium (CDISC) standards the analysis defines it as Day 1, i.e., Study Day=Date of assessment – Day of first post-partum ocrelizumab dose + 1. Study day will be defined in the footnotes of outputs as appropriate. The primary analysis time point will be described as the "Day 30 Visit" to highlight that it refers to the visit label defined in the protocol rather than the derived study day for analysis, since in this case the derived Study Day=31.

The analyses outlined in this Statistical Analysis Plan (SAP) supersede those specified in the protocol.

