4.8 SAFETY ANALYSES

The safety outcome measures to be analyzed comprise the following: incidence and nature of all adverse events (AEs), including findings on vital sign measurements, neurological examinations, clinical laboratory tests, and concomitant medications.

All safety analyses will be conducted on applicable data collected from the first postpartum ocrelizumab infusion until the end of the study. The safety analysis will be performed on the SAFM and infants (SAFI) separately.

4.8.1 Exposure of Study Medication

Definitions

Dose: Ocrelizumab dose is given as one infusion or two infusions administered 2 weeks apart. Patients will be considered to have received a Dose of treatment if at least part of one infusion of that Dose (either Day 1 or Day 15 for dual infusions) was given.

Treatment duration (in weeks) for a woman will be calculated as follows:

[(Date of last contact* – Date of first post-partum dose) + 1] / 7

- *Earliest 1) date of last OCR dose plus risk window of 6 months (182 days)
- 2) date of death
- 3) clinical cut-off date

Exposure Analysis

The following measures of exposure of ocrelizumab will be summarized in the SAFM using descriptive statistics:

- Number of patients completing each dose type (Dose 1, full dose; Dose 1 split dose #1; Dose 1, split dose #2)
- Treatment duration (weeks)

- Number of doses received (Day 1 and Day 15 infusions are considered as one dose)
- Total cumulative dose (mg)

A corresponding listing will be produced.

The analysis of exposure to ocrelizumab in infants (as measured via concentration in the breastmilk, and also directly from serum samples) is described previously as part of the primary and secondary endpoints.

4.8.2 Adverse Events

All summaries of AEs will be based on the respective safety population for mothers and infants, and will include AEs occurring between the mother's first post-partum ocrelizumab infusion and the end of the study. Only treatment-emergent AEs (TEAEs) will be analyzed and the terms TEAE and AE will be used interchangeably.

For each recorded adverse event (AE), the term entered by the investigator describing the event (the "reported term") will be assigned a standardized term (the "Preferred Term" [PT]) and assigned to a superclass term (the "System Organ Class" [SOC]) on the basis of the Medical Dictionary for Regulatory Activities (MedDRA) WHO dictionary of terms version 27.1.

Definitions

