Treatment-emergent adverse event (TEAE): AEs with an observed or imputed date of onset on or after the start date of trial treatment. If the onset date of the AE is prior to the day of first dose, the AE will be considered treatment-emergent only if the most extreme intensity is greater than the initial intensity (i.e., the intensity for a given AE increases and its end date is on or after the date of the first dose). An AE with a completely missing, non-imputed start date will be assumed to be treatment emergent unless the AE has a complete, non-imputed end date that is prior to the date of the first dose.

Imputation of incomplete date: in order to evaluate if an AE is treatment-emergent, incomplete dates will be imputed as follows:

- o If the start date is incomplete:
 - If the day is missing, impute to 01, or to the day of first dose of ocrelizumab if the month and year is the same as the dosing date.
 - If the month is missing, impute to January, or to the month of first dose of ocrelizumab if the year is the same as the year of dosing.
 - If the date is completely missing, then the date will remain missing
- o If the end date is incomplete:
 - If the day is missing, impute to the last day of the month
 - If the month is missing, impute to December
 - If the date is completely missing, then the date will be missing

If the imputed start date of an AE is post first dose, it is considered treatment emergent. If the imputed start date of an AE is prior first dose, it is considered non-treatment emergent.

In case of a missing start date and an (imputed) end date prior to first dose, the AE is considered non-treatment emergent.

Otherwise, the AE is considered treatment emergent.

Serious Adverse Events (SAEs): all SAEs including serious MS relapses and serious Infusion Related Reactions (IRRs).

Output Conventions

All analyses of AE data will be performed using the PTs unless otherwise specified.

For all summary tables, the AEs will be sorted by SOC (in decreasing order of overall incidence) and then by PT (in decreasing order of overall incidence). At each level of summarization (at least one event, SOC and PT), patients reporting more than one AE will be counted only once. For TEAEs by grade (intensity), the highest grade will be reported. All AE summaries will be based on TEAEs only.

The following summary tables will be generated for mothers and infants separately:

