- Overview summary table of TEAEs, including: total number of subjects with at least one AE, total number of AEs, total number of SAEs, total number of deaths, total number withdrawn from study due to an AE, and total number of subjects with at least one:
 - AE with fatal outcome
 - SAE
 - SAE leading to withdrawal from treatment ("Drug Withdrawn" for the "Action taken with ocrelizumab due to SAE/AE" field in the "Adverse Event/IRR" electronic Case Report Form [eCRF] form) (mothers only)
 - SAE leading to dose modification/interruption (mothers only)
 - Related SAE
 - AE leading to withdrawal from treatment (mothers only)
 - AE leading to dose modification/interruption (mothers only)
 - Related AE
 - Related AE leading to withdrawal from treatment (mothers only)
 - Related AE leading to dose modification/interruption (mothers only)
 - AE of Grade ≥3
 - Infusion related reaction (IRR) (mothers only)
 - Serious IRR (mothers only)

- Infections (using the MedDRA SOC of 'Infections and Infestations')
- Serious infections
- Serious infections leading to withdrawal from treatment (mothers only)
- TEAEs, by SOC and PT
- Serious TEAEs, by SOC and PT
- TEAEs, by Highest NCI CTCAE Grade
- Infections, by Type and PT (identified using the Orelizumab specific Adverse Events Glossary of Terms)
- IRRs, by Highest National Cancer Institute (NCI) Common Terminology Criteria for Adverse Events (CTCAE) grade (mothers only)
- Infusion Related Reactions by Time of Event (During Infusion, within 24 hours after end of infusion) Overall and by post-partum Infusion (Dose 1 full dose, Dose 1 split dose 1, Dose 1 split dose 2, Dose 2) (mothers only)
- Adverse Events of Special Interest (AESI, mothers only):
 - Cases of potential medicine-induced liver injury that include an elevated alanine transaminase (ALT) or aspartate transaminase (AST) in combination with either an elevated bilirubin or clinical jaundice, as defined by Hy's law and in the protocol.
 - Suspected transmission of an infectious agent by the study medicine, as defined in the protocol.

All SAEs, AESIs, AEs leading to withdrawal, infections, and deaths occurring during the study will be listed. For all of these listings, mothers/infants pairs will be presented 'next in line' as one row after the other in the same listing, rather than as two separate listings.

4.8.3 Laboratory Data

Laboratory assessments (performed in central laboratory, except for urinalysis) will include the following:

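### The SAP drops the adverse-event rates and 95% CIs that the protocol specifies, without declaring it, although infant time at risk can differ about 1.7-fold by age at entry

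*SAP*

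**What the plan says.** Protocol section 2 (Table 1) sets the infant safety endpoint as "Rate and nature of adverse events in the infant throughout the study, including infections and hospitalizations", with a parallel endpoint for mothers. Protocol 6.6.1, worded alike in version 4 (United States) and version 3, plans adverse-event summaries "including rates/incidence rates and corresponding 95% CIs".

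SAP 4.8.2 lists the adverse-event outputs. The overview table gives "total number of subjects with at least one AE, total number of AEs, total number of SAEs, total number of deaths", the number withdrawn, and the number of subjects with at least one event of each listed kind, including infections and serious infections. The other tables are by system organ class and preferred term, by highest grade, and by type of infection. In the summary tables, at each level, "patients reporting more than one AE will be counted only once". No table is given a rate over time, a CI or a separate row for hospitalizations.

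Two general rules in SAP section 4 bear on this: "For categorical variables, the number and percentage in each category will be displayed", and "Corresponding 95% confidence interval (CI) will be presented as appropriate". The same section says that the SAP's analyses supersede the protocol's. SAP section 5, which records changes from the protocol's analyses, contains one item, the renaming of an analysis set.

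SAP 4.2 derives time on study for mothers and infants, but no adverse-event table uses it.

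**The concern.** An analysis that the protocol names, and that matches the wording of the safety endpoint, does not appear in the document that governs the analysis, and no reason is given.

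It matters because infants are not followed for equal times. Eligibility fixes the infant's age at 2 to 24 "weeks of age at the time of the mother's first postpartum dose of ocrelizumab". Adverse events are summarised from that infusion, and collection ends at the last study visit, nominally about Month 13 of age. An infant whose mother is dosed late has less time in which to be counted. Without a time denominator, two cohorts with the same underlying infection rate can show different percentages merely because their entry ages differ. Without an interval, a reader may take a low or zero count among about 10 infants as firmer evidence than it is.

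**Working it through.** **Protocol and SAP side by side**

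| Item | Protocol | SAP 4.8.2 |
|---|---|---|
| Rate or incidence rate of AEs | named (6.6.1) | not named |
| 95% CI for AEs | named (6.6.1) | not named; only the general rule, as appropriate |
| Infections | named in infant endpoint | subjects with at least one; listing |
| Hospitalizations | named in infant endpoint | no row |
| Change declared | – | no (section 5) |

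**The plan's own interval figures.** No precision is stated for adverse events. The stated figures concern the B-cell endpoint with 10 infants (Protocol 6.2, SAP 2.2). Two-sided 95% Clopper-Pearson limits reproduce them:
- 1 event: 0.0025 to 0.4450, width 0.4425 (stated 0.443)
- 2 events: 0.0252 to 0.5561, width 0.5309 (stated 0.531)
- 0 events: upper limit 0.3085 (stated 0.31)

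In that passage the plan uses event rate for a simple proportion, which bears on the objection below.

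**Infant time at risk.** Follow-up = age at last visit minus age at the mother's first post-partum infusion. Inputs: entry at 2 to 24 weeks (Protocol 4.1.1); last visit at Month 13, with a window of 30 days, or one month after an MMR dose (SAP 2.3). With 1 month = 365.25/12 days, Month 13 = 13 × 30.4375 / 7 = 56.53 weeks.
- Entry at 2 weeks: 56.53 − 2 = 54.53 weeks
- Entry at 24 weeks: 56.53 − 24 = 32.53 weeks
- Ratio: 54.53 / 32.53 = 1.68

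Other last-visit ages, the same for both infants:
- 12 months (MMR at 11 months, sampled one month later): 50.2 / 28.2 = 1.78
- Month 13 plus 30 days: 58.8 / 36.8 = 1.60
- 16 months (an assumed late MMR dose): 67.6 / 45.6 = 1.48

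**Effect on a subject percentage.** At a constant rate r per year, P(at least one event) = 1 − exp(−r × weeks / 52.18). The values of r are assumed.

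| r per year | Entry at 24 weeks | Entry at 2 weeks |
|---|---|---|
| 0.5 | 27% | 41% |
| 1 | 46% | 65% |
| 2 | 71% | 88% |

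**What the restored output would show.** Ten infants followed to Month 13; event counts assumed. Exact Poisson limits are χ²(0.025; 2k)/2 and χ²(0.975; 2k+2)/2, each divided by infant-years.

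| Entry age | Infant-years | Rate for 5 events (95% CI) | Upper limit for 0 events |
|---|---|---|---|
| all 2 weeks | 10 × 54.53 / 52.18 = 10.45 | 0.48 (0.16 to 1.12) | 0.35 |
| mean 13 weeks | 10 × 43.53 / 52.18 = 8.34 | 0.60 (0.19 to 1.40) | 0.44 |
| all 24 weeks | 10 × 32.53 / 52.18 = 6.23 | 0.80 (0.26 to 1.87) | 0.59 |

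If the five events fall in five different infants, the planned table reads 5 (50%) in all three rows. Its exact binomial 95% CI would be 18.7% to 81.3%; for 0 of 10 the upper limit would be 30.8%. Neither interval is planned.

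**The case against.** The best defence is that this is an under-specified output rather than a substitution. The general rule adds percentages to the counts, CIs are allowed where appropriate, and SAP 4.8 still speaks of the incidence of adverse events. Neither document mentions person-time for adverse events, and the sample-size text uses event rate for a proportion. A percentage with a binomial CI could therefore arguably meet the protocol. That stands in part: the documents do not oblige the sponsor to use person-years, and it would be wrong to say that only bare counts are planned. It does not supply the missing CI. The protocol has a similar general sentence on CIs and still names adverse-event rates and CIs separately, and where the SAP wants a time-based rate it says so (annualized relapse rate, 4.6.3).

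Three stronger readings are tempting and are not supported:
- **Comparison with background rates is impossible.** It is not. Time on study is summarised, and all infections and SAEs are listed, so crude rates can be rebuilt by hand. Nor is such a comparison planned or the only use of the data; the paired mother-infant listings serve case review.
- **Treatment duration in SAP 4.8.1 is a faulty denominator.** It is defined for the woman as an exposure measure, and the SAP never divides adverse events by it.
- **Hospitalizations go unseen.** Inpatient hospitalization is a seriousness criterion (Protocol 5.1.1.2), so most will fall within the SAE tables. They are only not shown separately.

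It is also fair that these are descriptive tables on about 10 infants, and that the 1.68 compares the two extreme permitted entry ages. The actual spread is unknown.

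**Conclusion.** The point holds as an undeclared gap between protocol and SAP in the safety analysis. It touches neither co-primary endpoint and loses no data, but it should be corrected, because what is dropped is the analysis that matches the endpoint. The planned percentages mix entry age with event rate: at an assumed one event per year, the chance of being counted is 46% at one end of the entry range and 65% at the other. The 1.68 ratio assumes a last visit at Month 13 for both infants and no early withdrawal. The event rates and counts are illustrations, since the documents give none.

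**What to change.** In SAP 4.8.2 add one table, for mothers and infants separately, covering all AEs, SAEs, infections, serious infections and hospitalizations. For each, give:
- n (%) of subjects with an exact binomial 95% CI
- number of events, person-years, and events per person-year with a 95% CI

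Count person-time from the mother's first post-partum infusion to the subject's last study visit or discontinuation. This is the SAP 4.2 time on study with one adjustment: that definition can run to the latest recorded date in any data, whereas adverse events are collected to the last study visit (Protocol 5.1.2.1), so the end date should be aligned.

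Label exact Poisson intervals as descriptive. They treat events as independent, and repeat infections in one infant can make them too narrow.

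If the sponsor prefers not to give rates, SAP section 5 should state the change and the reason.

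The cost is one additional table from data already collected, with wide intervals at about 10 infants.

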4.8.3.1 General Laboratory Evaluation and Reporting Conventions

All laboratory assessments in the mother (hematology, serum chemistry, urinalysis, Hepatitis B virus serology, serum immunoglobulin concentration) will be summarized in the SAFM or listed when applicable.

Absolute value and change from baseline at each visit will be summarized using standard unit. The baseline value for laboratory assessments summarized in mothers will be the last value prior to the first dose of study medication. When laboratory data are presented over time, these laboratory values will be time-windowed into a common visit structure. If multiple values of the same laboratory parameter occur within the same time window, the worst value for that parameter will be presented in the summary table.

Unless specified otherwise, any laboratory parameters which are below the BLQ will be listed, for summaries a value of the LLQ/2 will be imputed. Values above the upper limit of quantification will be summarized at the upper limit of quantification.

For hematology and serum chemistry, the number and percentage of patients with normal/abnormal laboratory outcomes based on normal laboratory ranges will be summarized for each parameter and visit. For urinalysis, the number and percentage with each test result category will be reported for each parameter and visit.

Corresponding patient-level listings will be produced for the following in the SAFM: hematology, serum immunoglobin concentration, laboratory abnormalities for hematology, laboratory abnormalities for serum chemistry, laboratory abnormalities for urinalysis.

